9.2 Sample Size Determination

[Part A / Part C]

Due to the exploratory nature of the study, the sample size is not based on formal statistical considerations, but on experience from similar Phase I studies previously conducted with other compounds. Eight Japanese subjects on active drug are considered to be sufficient to confirm a tendency for safety, PK, and PD data.

[Part B]

The primary endpoint is assumed to follow a log-normal distribution with a standard deviation of 0.3. Under these assumptions, at least 18 evaluable patients per arm yield more than 95% power to detect a difference of 0.693 on the log-scale (corresponding to 50% relative reduction) compared to placebo in a two-sided t-test at a 5% significance level. The same number of evaluable patients would provide approximately 89% power to detect a difference of 0.33 between the **CCI** group and **CCI** group. Accounting for 10% drop-out, 60 patients in total will be randomized.

Note: “Enrolled” means a participant’s, or their legally acceptable representative’s, agreement to participate in a clinical study following completion of the informed consent process. Potential participants who are screened for the purpose of determining eligibility for the study, but are not randomly assigned/assigned in the study, are considered “screen failures”, unless otherwise specified by the protocol.

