9.4.2 Efficacy

[Part B]

The analysis and presentation of efficacy and exploratory endpoints will be based on participants in the full analysis set.

For selected efficacy variables, if not specified otherwise, a mixed model for repeated measures will be fitted using log-transformed data and results transformed back to geometric mean ratios for the purpose of presentation and interpretation. The mixed model for repeated measures will include the relevant log-transformed baseline biomarker value as a covariate. Time point (visit number), treatment, and the interaction between time point and treatment will be included as factors. The response variable will be change from baseline in log-transformed biomarker value. The model will be fitted with an unstructured covariance structure, and the Kenward-Roger correction applied to obtain the degrees of freedom. Estimation of the treatment effect will be done for each visit after baseline. In case of issues when fitting the model to the data, a hierarchical model fitting procedure will be described in the statistical analysis plan.

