4.2.1.4 Primary Analysis of Primary Endpoint

The analysis and presentation will be based on subjects in the Full Analysis Set.

The study hypothesis to be tested is treatment effect of AZD8233 across different dose levels [REDACTED] compared to placebo. The null hypotheses for these tests are that the absolute change in log-transformed LDL-C for AZD8233 at some dose level is equal to the absolute change in log-transformed LDL-C for placebo.

A mixed model with repeated measures will be fitted using the log-transformed LDL-C data. The model will include the log-transformed LDL-C baseline value as a covariate and time point (visit number), treatment, and the interaction between time point and treatment will be included as factors. The response variable will be change from baseline in log-transformed LDL-C. The model will be fitted with an unstructured covariance structure, and the Kenward-Roger correction applied to obtain the degrees of freedom. The primary model will include data up to and including Week 12 as a response variable.

Estimation of the treatment effect will be calculated for each visit after baseline and presented alongside the corresponding 95% confidence interval. In case of issues when fitting the model to the data, the following hierarchical model fitting procedure will be adopted:

1. The MMRM will be fitted using a spatial power covariance structure; Visit will be expressed as scheduled visit days to accomplish the variance-covariance matrix estimation.
2. The MMRM will be fitted using a compound symmetry covariance structure.
3. An ANCOVA model for Week 12 only will be used.

Comparisons of the change from baseline between the treatment groups will be conducted using the least square mean difference (LSMD) between treatment groups as estimated by

the fitted model. Pair-wise comparisons will be done for each AZD8233 dose [REDACTED] vs. placebo. In addition, pair-wise comparisons between AZD8233 dose groups [REDACTED] will also be done for reference. The p-value for each comparison will be presented alongside the LSMD and its 95% CI. In addition, LSMs and 95% CIs will be back-transformed to present as relative (geometric) difference among treatment groups and the relative change will also be presented as the percent change from baseline.

Change from baseline will be summarized by visit and treatment groups using descriptive statistics (arithmetic mean, SD, minimum, median, maximum) and based on the principles defined in Section 3.3.

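### If the unstructured MMRM cannot be fitted, the first two fallbacks force one variance on all seven visits, so the Week 12 interval can be too narrow or too wide

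*SAP*

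**What the plan says.** SAP Part B section 4.2.1.4 models change from baseline in log LDL-C with an unstructured covariance and Kenward-Roger degrees of freedom, using all visits up to Week 12. From the schedule these are Days 8, 22, 29, 43, 57, 71 and 85, so seven visits.

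If there are fitting problems, the SAP lists three steps in order:

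1. "The MMRM will be fitted using a spatial power covariance structure", with visit entered as scheduled day.
2. "The MMRM will be fitted using a compound symmetry covariance structure".
3. An ANCOVA at Week 12 alone.

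On the fixed effects, "The model will include the log-transformed LDL-C baseline value as a covariate and time point (visit number), treatment" and the visit-by-treatment interaction. Protocol section 9.4.2 has the same terms: "Time point (visit number), treatment, and the interaction between time point and treatment will be included as factors". Neither document has a baseline-by-visit term.

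Protocol section 9.4.2 leaves the fallback list to the SAP. The sensitivity analyses in SAP section 4.2.1.5 vary the population and the missing-data assumption, but not the covariance structure. SAP sections 4.2.1.6, 4.2.2.4 and 4.2.3.4 reuse the primary model for the supplementary LDL-C measures, PCSK9 and percent change in LDL-C.

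**The concern.** Spatial power and compound symmetry each have two parameters: one variance and one correlation. Neither lets Week 12 have its own variance. Because the model has a treatment effect at every visit, the Week 12 point estimate barely changes between structures, but its standard error is built from a variance pooled over visits. Kenward-Roger adjusts for estimating the covariance parameters. It does not correct a structure that is wrong. The ANCOVA, which uses only Week 12 data, is free of the problem, but it is reached only if two very simple structures also fail.

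Constant variance cannot be taken for granted. Day 8 follows a single dose, while protocol section 4.3 expects near steady state only about 12 weeks after the start of dosing. SAP section 4.2.1.1 also changes the LDL-C method when the Friedewald value is below 40 mg/dL. Both are reasons to expect visit-dependent spread, but they are inference and do not fix its direction.

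At stake are the reported Week 12 interval and the comparison between the two active doses.

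**Working it through.** **The plan's own figures.** Protocol section 9.2: "The primary endpoint is assumed to follow a log-normal distribution with a standard deviation of 0.3"; "at least 18 evaluable patients per arm yield more than 95% power to detect a difference of 0.693 on the log-scale"; "approximately 89% power to detect a difference of 0.33" between doses; all "in a two-sided t-test at a 5% significance level".

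- Standard error of a difference with 18 per arm: 0.3 × √(2/18) = 0.10.
- Noncentrality: 0.693/0.10 = 6.93 and 0.33/0.10 = 3.3, with 34 degrees of freedom.
- Power: above 99.99% and 89.4%. Randomized total: 54/0.9 = 60. All agree with the protocol.

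**Effect of a single variance.** Inputs: Week 12 SD 0.30 (the plan's value, used here as the residual SD), and SDs at the other six visits that are assumed, in equal steps from Week 1 to Week 12.

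- SE ratio = √(mean of the seven squared SDs) / 0.30
- Coverage = 2Φ(1.96 × ratio) − 1

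For a rise from 0.20 to 0.30, the squared SDs sum to 0.4453. The mean is 0.0636 and its root 0.252, so the ratio is 0.84 and coverage 90.1%. The other profiles follow in the same way. The simulated column gives the range over both fallbacks and two correlation shapes (3 × 18 complete cases, baseline log SD assumed 0.25, 400 runs each).

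| Assumed SD, Week 1 to Week 12 | SE ratio | Coverage, formula | Coverage, simulated |
|---|---|---|---|
| 0.30 flat | 1.00 | 95.0% | 94.5-95.5% |
| 0.20 rising to 0.30 | 0.84 | 90.1% | 90.5-92.0% |
| 0.15 rising to 0.30 | 0.77 | 86.8% | 86.2-88.2% |
| 0.40 falling to 0.30 | 1.17 | 97.8% | 97.0-97.2% |

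Monte Carlo error is about 2 to 3 points, and the simulation used fixed degrees of freedom rather than full Kenward-Roger. In the same runs the Week 12 ANCOVA gave 94-96%, as did the unstructured model with a common slope.

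A further analytic check took the best-fitting version of each structure under three true correlation shapes, with the SD linear in day. It gave 90%, 86-87%, 95% and 98% for the corresponding profiles. Heterogeneous AR(1) stayed at 95.0-95.5% throughout, although it ignores the unequal visit spacing.

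**What this does to the interval.** The correct half-width is about 1.96 × 0.10 = 0.196 on the log scale. Multiplied by the ratios 0.84, 0.77 and 1.17, the reported half-width would be about 0.165, 0.151 or 0.229.

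**Shared baseline slope.** If the Week 12 slope differs from the common slope by d and log baseline has SD s, the Week 12 variance rises by the factor 1 + d²s²/0.09. With s = 0.25 (assumed):

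- d = 0.1 gives 1 + 0.01 × 0.0625/0.09 = 1.007.
- d = 0.2 gives 1 + 0.04 × 0.0625/0.09 = 1.028.

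Simulated variance ratios were 0.99-1.00 with no slope change, 1.01 for slopes running from −0.15 to −0.35, and up to 1.08 for −0.10 to −0.50. The last can exceed 1.028 because the fitted common slope is a weighted one and need not sit at the midpoint.

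**The case against.** The strongest reply is that the fallback may never be used. The unstructured model is primary. In a small check with 60 participants, seven visits, 10% dropout and 2% sporadic missing values under an assumed correlation, it converged to a positive-definite matrix in 100 of 100 simulated trials. That used a purpose-written REML routine, not SAS, but it suggests a rarely taken branch. This stands and limits the weight of the point.

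A reader might infer that the Week 12 interval would be too narrow. The documents do not support a direction. They give one SD and none by visit, and a falling profile makes the interval too wide.

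A reader might also infer that the primary conclusion is unsafe. At the planned 0.693 it is not: a 23% error in a standard error of 0.10 cannot overturn a difference of nearly seven standard errors. The between-dose contrast is closer to the margin, but protocol section 9.4.2.1 and SAP section 4.2.1.4 make it for reference only.

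A third reply defends spatial power, because it uses the actual visit days and the gaps are unequal (7 days between Days 22 and 29, otherwise 14). That is a fair reason not to insist on deleting it. But the correlation shape hardly matters for Week 12 coverage, whereas the Week 12 variance does.

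Finally, the shared slope is not a source of bias in a randomized comparison. Nothing in the documents shows that the slope changes by visit, and the precision at issue is small.

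**Conclusion.** The point holds as a conditional weakness in the fallback list, and nothing elsewhere in the plan repairs it. If the unstructured fit fails, the next two steps give a correct Week 12 interval only under constant variance. Over the assumed profiles, coverage runs from about 86% to 98%. These figures rest on a Week 12 residual SD of 0.30, assumed SDs at the other visits, and about 18 complete cases per arm.

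The likelihood of reaching the fallback is probably low, and the placebo conclusion at the planned effect is not exposed. What is exposed is the reported interval, and the between-dose contrast that informs dose selection. It merits a change because the remedy costs almost nothing. The baseline-by-visit term is a separate, optional refinement.

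**What to change.** In SAP Part B section 4.2.1.4, reorder the fallback list:

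1. Heterogeneous Toeplitz, then heterogeneous AR(1); or spatial power with visit-specific variances, to keep the unequal spacing.
2. Spatial power or compound symmetry with a single variance, if kept at all, only with a sandwich standard error. State the degrees-of-freedom method for that step, because Kenward-Roger works from the model-based covariance.
3. Week 12 ANCOVA as the last step.

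Apply the same list to the other MMRMs (SAP sections 4.2.1.6, 4.2.2.4, 4.2.3.4 and 4.2.4.4).

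The cost is SAP wording and a few more covariance parameters: 7 variances + 1 correlation = 8 for heterogeneous AR(1), against 2 for the present fallbacks and 7 × 8/2 = 28 for unstructured. The order-based structures ignore the 7-day gap, which barely affects Week 12 coverage.

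Optional: add baseline log LDL-C by visit. Because protocol section 9.4.2 fixes the model terms, record this in SAP section 2 as a change from the protocol. It costs six fixed-effect parameters. It usually gains about 1% of Week 12 variance or less, and up to 8% only if the baseline slope changes strongly over visits.

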4.2.1.5 Sensitivity Analyses of the Primary Endpoint

Sensitivity analysis 1 will consist of repeating the MMRM assuming a log-normal distribution including only subjects who have completed the treatment period as per protocol and who have no relevant IPDs. Subjects who have completed the treatment period as per protocol are the subjects who reached week 12 and received all three scheduled doses of IP; subjects who received the wrong dose of IP or wrong treatment will be excluded. Further, relevant IPDs are defined section 3.3.5.

Sensitivity analysis 2 will consist of repeating MMRM assuming a log-normal distribution (without any back-up strategy) using the pattern-mixture model with control-based pattern imputation, if more than 20 % of data is missing this analysis will be considered.

To implement this approach, the MCMC will be used firstly to impute non monotone MAR missing data for subjects who have completed the treatment period as per protocol (reached week 12 and received all three doses of IP). Then the resulting dataset will be used to sequentially impute missing data at each visit using a monotone regression approach. Sequential imputation will be done in two ways:

1. Considering only placebo group for the estimations of missing data for placebo patients and for AZD8233 subjects at visits for which the previous scheduled dose of IP is missing or not as per protocol (wrong dose of IP or a wrong treatment)

2. Considering only the relevant AZD8233 group for the estimations of missing data for AZD8233 subjects at visits for which the previous scheduled dose of IP was taken as scheduled.

The results from each imputation set will be combined using Rubin's formulas (reference 1).

4.2.1.6 Supplementary Analyses of the Primary Endpoint

LDL-C derived by the Friedewald formula without reflex, LDL-C derived by the Martin/Hopkins formula and direct LDL-C will be analysed as described in section 4.2.1.4 above and presented as a supplementary analysis of the primary endpoint.

4.2.1.7 Subgroup Analyses

Not applicable.

4.2.2 Secondary Endpoint- Absolute change from baseline in log-transformed PCSK9 in plasma and percent change from baseline in PCSK9 in plasma

4.2.2.1 Definition

Not applicable.

4.2.2.2 Derivations

PCSK9 measurement will be assigned to analysis visits as described in Section 3.3.2. Measurements below the LLOQ for which the exact value cannot be determined will be replaced by the LLOQ divided by the square root of 2. After replacement of LLOQ, the absolute change and percent change from baseline are calculated for each study visit.

Change from baseline of the log-transformed variable is calculated as the visit value in natural logarithm minus the baseline value in natural logarithm. Percent change from baseline is calculated using the raw values as the visit value minus the baseline value divided by the baseline value *100.

4.2.2.3 Handling of Dropouts and Missing Data

Missing data will not be imputed and only observed values will be reported in the summary tables and listings. Treatment discontinuation visit will be mapped according to Section 3.3.2.

4.2.2.4 Primary Analysis of Secondary Endpoint

The absolute change from baseline in the log-transformed PCSK9 will be fitted using the mixed model for repeated measures as described for the primary endpoint (refer to section 4.2.1.4), such that the model includes the log-transformed baseline value as a covariate, time point (visit number), treatment, and the interaction between time point and treatment as

factors. The least square mean differences between treatment groups will be estimated from the fitted model and presented alongside the corresponding 95% confidence interval. In addition, LSMs and 95% CIs will be back-transformed to present as relative (geometric) difference among treatment groups and the relative change will also be presented as the percent change from baseline.

The summary and corresponding plot of the absolute change from baseline will be generated using the same method described for the primary endpoint (refer to Section 4.2.1.4).

The percent change from baseline in PCSK9 will be analyzed using the same model as described previously without log-transformation. In addition, the summary and plot will be made using the same method.

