of Week 12 with or without inclusion of the loading dose, ie for a once monthly dosing regimen. This is in line with preliminary estimates of the terminal half-life of AZD8233 full length ASOs in plasma (2-3 weeks) that indicate that close to pharmacokinetic steady state should have been reached 12 weeks after start of dosing. Thus the effect of a loading dose will be marginal, and therefore there will be no additional dose one week after the initial dose of AZD8233 in Part B.

The safety data and potentially the PCSK9 and LDL-C data after repeated (Days 1, 8, 29, and 57) dosing of AZD8233 up to **CCI** from other AZD8233 studies (including the ongoing D7990C00002 and D7990C00003 studies) will have been evaluated before the doses of Part B will be finally selected. Based on such emerging data of AZD8233, the planned doses in Part B may be slightly adjusted if needed to achieve the intended PCSK9 and LDL-C reduction. However, the highest dose will not exceed **CCI** (Days 1, 29, and 57), which is lower than the highest dose in the ongoing MAD study and the dose in Part A.

[Part C]

AZD8233 **CCI** will be assessed in Part C. The efficacy and safety of **CCI** and **CCI** were assessed in global phase 2 study (D7990C00003) with 3 months treatment and **CCI** is evaluated in an ongoing phase 2 study with 6 months treatment (D7990C00004). Based on the results from the global phase 2 study, the **CCI** dose resulted in a larger mean LDL-C reduction (-79% (95% CI; -83, -74)) than the **CCI** dose (-72% (95% CI; -78, -65) indicating that **CCI** dose is not fully on the plateau of the max achievable effect. Therefore, if the **CCI** dose is confirmed as well tolerated and no significant safety concerns are raised, the **CCI** is the dose planned to be selected for the phase 3 study program. The safety and tolerability of **CCI** is therefore planned to be assessed in Part C.

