4.2.1.2 Derivations

LDL-C values will be assigned to analysis visits as defined in Section 3.3.2. Measurements below the LLOQ for which the exact value cannot be determined will be replaced by the LLOQ divided by the square root of 2.

Change from baseline of the log-transformed variable will be calculated as the visit value in the natural logarithm minus the baseline value in natural logarithm.

Percent change will be derived from the MMRM estimates as:

$$\text{Mean percent change} = 100 * (\exp(\text{LSMean}) - 1)$$

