4.2.3 Secondary Endpoint- Percent change in levels of LDL-C in serum

4.2.3.1 Definition

Percent change from baseline in LDL-C will be calculated on the raw scale for each subject. Reflex LDL-C will be primarily assessed and the direct LDL-C or other quantification may be considered in sensitivity analyses (refer to Section 4.2.1.1).

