4.2.3.4 Analysis of Secondary Endpoint

LDL-C will be analyzed using the statistical model described for the primary endpoint (refer to Section 4.2.1.4).

LDL-C endpoints will be summarized by visit and treatment group using descriptive statistics (arithmetic mean, SD, minimum, median, maximum) using the principles defined in Section 3.3.

The plot of LSMean (95% CI) based on the MMRM estimates will be produced.

Percent change from baseline for direct LDL-C will be analysed similarly.

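### Part B raw percent-change MMRMs for LDL-C and PCSK9 pool one covariance over arms, which miscalibrates the Week 12 confidence intervals under the plan's own log-normal assumption

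*SAP*

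**What the plan says.** The primary analysis of Part B is an MMRM of change in log LDL-C with baseline, visit, treatment and their interaction. On the covariance, SAP Part B 4.2.1.4 says: "The model will be fitted with an unstructured covariance structure, and the Kenward-Roger correction applied to obtain the degrees of freedom". It names no grouping by treatment.

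Two secondary endpoints reuse this model on the raw percent scale. For PCSK9, SAP Part B 4.2.2.4 states: "The percent change from baseline in PCSK9 will be analyzed using the same model as described previously without log-transformation". For LDL-C, 4.2.3.1 states: "Percent change from baseline in LDL-C will be calculated on the raw scale for each subject", and 4.2.3.4 adds: "LDL-C will be analyzed using the statistical model described for the primary endpoint". Protocol 9.4.2.2 also asks for an original-scale LDL-C percent-change MMRM.

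The log-scale models yield percent changes too. SAP Part B 4.2.1.2 introduces the back-transformation for LDL-C with "Percent change will be derived from the MMRM estimates as", and 4.2.2.4 says for PCSK9 that "the relative change will also be presented as the percent change from baseline". Each marker therefore gets two model-based percent-change results.

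On variability, Protocol 9.2 says: "The primary endpoint is assumed to follow a log-normal distribution with a standard deviation of 0.3".

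**The concern.** A log-normal endpoint with one log SD cannot also have one SD on the percent scale. The SD of percent change is proportional to the level that remains, so a drug that removes most of the LDL-C or PCSK9 also removes most of the percent-scale spread. A pooled covariance averages a wide placebo arm with narrow active arms. The standard error is then too small for active versus placebo and too large for dose versus dose. The Kenward-Roger correction works within the assumed covariance and does not make it arm-specific. The SAP plans no sensitivity analysis for PCSK9 that would reveal the problem (4.2.2.5, 4.2.2.6).

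What is at stake is the calibration of intervals on named secondary endpoints. A raw-scale dose contrast could also look inconclusive beside a clear log-scale one, in a study part meant to inform dose selection.

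**Working it through.** **Plan's own figures (Protocol 9.2).** With SD 0.3 and 18 per arm, the standard error of a log-scale difference is 0.3 × √(2/18) = 0.10. A difference of 0.33 gives noncentrality 3.3 on 34 df and power 89.4%, matching the stated 89%. For 0.693 power exceeds 99.9%. Then 54/0.9 = 60. All reproduce.

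**Percent-scale SDs.** With log SD s and remaining fraction G, SD = 100 × G × exp(s²/2) × √(exp(s²) − 1). At s = 0.3 this is 32.1 × G. Taking placebo at no change, low dose at 50% reduction (0.693) and mid dose at 64% (exp(−0.693 − 0.33) = 0.36) gives 32.1, 16.1 and 11.6 points. Protocol 9.2 gives 0.693 and 0.33 only as differences to detect, so this placement is an inference.

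**Pooled versus actual standard error, 18 per arm.**
- Pooled SD = √[(32.1² + 16.1² + 11.6²)/3] = 21.8, so the standard error is 21.8 × √(2/18) = 7.3 for every contrast.
- Low dose versus placebo: √[(32.1² + 16.1²)/18] = 8.5.
- Mid dose versus placebo: √[(32.1² + 11.6²)/18] = 8.0.
- Dose versus dose: √[(16.1² + 11.6²)/18] = 4.7, so the pooled value is about 1.5 times too large.

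**Simulated coverage.** Week 12 ANCOVA with a baseline covariate and one pooled variance (the complete-data analogue of the MMRM), 18 per arm, 10,000 replicates. Only the LDL-C log SD of 0.3 is documented. The other SDs, and the use of these reductions for these arms, are assumptions. The 72%/79% pair comes from the global phase 2 study in Protocol 4.3, where the higher dose "resulted in a larger mean LDL-C reduction (-79% (95% CI; -83, -74".

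| Endpoint, low/mid reduction | Log SD placebo/active | Coverage versus placebo, low / mid | Dose-contrast width relative to arm-specific |
|---|---|---|---|
| LDL-C 30%/50% | 0.3/0.3 | 91.9% / 93.8% | 1.2 |
| LDL-C 50%/64% | 0.3/0.3 | 90.4% / 91.7% | 1.5 |
| LDL-C 72%/79% | 0.3/0.3 | 88.6% / 89.1% | 2.2 |
| LDL-C 50%/64% | 0.3/0.4-0.5 | 92.0-92.4% / 93.8-95.3% | 1.07-1.22 |
| LDL-C 30%/50% | 0.3/0.4-0.5 | 92.6-93.8% / 95.7-97.0% | 0.95-1.04 |
| LDL-C 72%/79% | 0.3/0.45 | 89.9% / 91.0% | 1.6 |
| PCSK9 75-79%/90% | 0.2/0.5 | 89.7-90.4% / 92.9-94.3% | 1.3-1.4 |

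For PCSK9 at 75%/90% with the LDL-C value of 0.3 borrowed for all arms, a separate simulation without the covariate gives 88.4% / 88.9%.

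In the planning case (second row) the dose contrast has half-width 14.5 points against 9.8 with arm-specific variances. It covers above 99% and rejects about 52% of the time, against about 87% with arm-specific variances and 90% on the log scale. Arm-specific variances give coverage of 94.0-96.5% over all scenarios and contrasts run.

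**Could active-arm log SDs be larger?** The global phase 2 intervals have log half-widths ln(0.26/0.17)/2 = 0.21 and ln(0.35/0.22)/2 = 0.23. If these are within-arm changes with 18-20 per arm (n is not given), half-width × √n / 1.99 implies a log SD of about 0.45-0.52. If they are placebo-corrected with placebo SD 0.3, it is 0.34-0.43.

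**The same check on the log scale.** With placebo/active log SDs of 0.3/0.45, the pooled SD is √[(0.09 + 2 × 0.2025)/3] = 0.41. The pooled standard error is 0.135, against an actual 0.150 for dose versus dose. Simulated coverage is 96.2% versus placebo and 92.4% for the dose contrast. With 0.2/0.5 it is 96.9% and about 90%.

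**The case against.** The strongest reply is that nothing decided by the trial turns on this. Raw-scale point estimates are essentially unbiased (at most 0.15 points). With no effect and equal log SDs the percent-scale SDs are equal too, and rejection is 5.0-5.1%. Rejection versus placebo is 98.9-100% at the planning effects or larger. The dose contrast is for reference only (Protocol 9.4.2.1), and no multiplicity-controlled claim rests on these intervals (SAP Part B 3.3.4). All of this stands and limits the weight of the point.

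A second reply is that size and direction are not established. This also stands: the LDL-C scenarios fall on both sides of 95%, and the ranges are not bounds. At 50%/72% with log SDs 0.2/0.5, LDL-C coverage reaches 97.9%. What remains is that the one SD the documents supply leads to under-coverage versus placebo.

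Two stronger readings are tempting, and the documents do not support them. A reader might infer that the plan leaves open which scale governs. In fact SAP Part B 4.2.1.1 makes log-scale LDL-C primary, and the protocol synopsis makes the log-scale PCSK9 comparison the key secondary objective. Only the choice of which percent-change interval to quote is open. A reader might also infer that the back-transformed log-scale results are free of the problem. They use the same single covariance and are correctly calibrated only if log SDs are similar across arms.

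**Conclusion.** The point holds as a calibration problem worth correcting, not as a threat to the trial's conclusions. Under a common log SD of 0.3, with doses inferred at 50% and 64% reduction and 18 per arm, raw-scale intervals versus placebo cover about 90-92% and the dose-versus-dose interval is about 1.5 times too wide. At 72%/79% for LDL-C, or 75%/90% for PCSK9 with the borrowed SD, coverage versus placebo is about 88-89%. If active arms are more variable than placebo on the log scale, the raw-scale error shrinks or reverses, and the log-scale dose contrast becomes the one that under-covers, at about 90-92%. Because the documents give no arm-specific SDs and no PCSK9 SD, neither scale can be assumed safe in advance.

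**What to change.** In SAP Part B 4.2.2.4 and 4.2.3.4, keep the raw percent-change MMRM, which the protocol requires for LDL-C. Base the intervals and p-values for its Week 12 contrasts on arm-specific variances with Satterthwaite degrees of freedom, or on robust standard errors. Report the same variance check for the log-scale Week 12 contrasts.

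Optionally, add a sentence saying which percent-change estimate will be quoted, noting that the raw result is an arithmetic mean change and the back-transformed one a geometric mean change.

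The cost is one extra Week 12 output per endpoint and somewhat wider raw-scale intervals versus placebo: in the LDL-C planning case the half-width goes from 14.5 to 17.2 points for the low dose and 16.4 for the mid dose. A full unstructured covariance per arm is not the lead proposal. Seven post-baseline visits to Week 12 need 7 × 8/2 = 28 parameters per arm, or 84 from 54-60 participants.
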